5.4.1.3. Discontinuation of omega-3 EPA/DHA concentrate

Subjects would be continuously evaluated for any untoward effects of Omega-3 fatty acid supplements or negative side effects. Typically side effects consist of minor gastrointestinal symptoms, such as belching, indigestion, or diarrhea, stomach pain or discomfort, burping, heartburn, vomiting, constipation, nausea, and change in the sense of taste. Joint pain may be a side effect as well.

Patients with coagulation, bleeding, or blood disorders will be excluded. We will monitor clotting times of enrolled subjects by measuring the prothrombin time (PT/PT-INR) during all subject visits (except for visit 1), in addition to CBC with differentials (see schedule of assessment).

Symptomatic management of the side effects will be evaluated by the study physician and should the investigator believes that the study treatment is no longer in the best interest of the participant, subjects would be discontinued from the treatment. Similarly, if subject begins taking medications that affect clotting chronically, subjects would be discontinued and appropriately noted in the study record. Participants who prematurely discontinue study treatment will remain in the study and undergo all efficacy and safety assessments.

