5.4.2.2. Modification or Discontinuation of Vitamin D

Vitamin D is likely safe when taken by mouth in recommended amounts. Most people do not commonly experience side effects with vitamin D, unless too much is taken. Some side effects of excess vitamin D include weakness, fatigue, sleepiness, headache, loss of appetite, dry mouth, metallic taste, nausea, and vomiting.

Taking vitamin D for long periods of time in doses higher than 4000 units daily is possibly unsafe and may cause excessively high levels of calcium in the blood. However, much higher doses are often needed for the short-term treatment of vitamin D deficiency.

Vitamin D in very high doses can make the intestines absorb too much calcium which can cause high levels of calcium in the blood (hypercalcemia). This can cause side effects including nausea, vomiting, constipation, poor appetite, weakness, weight loss, confusion and disorientation. Hypercalcemia can also lead to kidney stones, damage to the kidneys, and cause calcium deposits in heart and lungs. We will monitor blood levels of vitamin D to minimize the risk of these side-effects.

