5.4.5. Removal of Subjects from Therapy or Subject Withdrawal or Early Termination

- **Withdrawal of consent** - Participants who withdraw consent will be asked to complete all the assessments listed for the end of treatment follow-up
- **Failure to return** - Participants who do not return for visits and who do not respond to repeated attempts by the site staff to have them return will be considered lost to follow-up.
- **Investigator judgment** - A severe or serious AE occurs, which, based on the medical judgment of the investigator, prevents completion of participation in the study.

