5.4.6. Discontinuation of study drug(s) in an individual patient

The dosing and administration of investigational medication according to study specification will be discontinued for an individual participant if any of the following criteria is met:

- Subjects who have 3 severe hypoglycemic reactions on separate days (requiring assistance from another individual)
- Subjects who have nausea or vomiting that precludes adherence to diet will discontinue the use of the study drug.
- Subjects who lose more than 10 kg in weight from baseline.

- Any grade 3 or higher AE occurs that, based on the medical judgment of the investigator, the medical monitor, and the clinical trial physician, prevents completion of the course of study treatment.
- Any unexpected, treatment-related SAE resulting in permanent treatment discontinuation and not related to glycemic events.
- The investigator determines that it is in the participant's best interest to discontinue treatment.
- The participant, or participant's legal representative, requests that treatment be halted.
- The participant becomes pregnant.

Further care will be provided according to the judgment and practice of the investigator. The participant will be asked to remain in the study and participate in follow-up. If study treatment is discontinued, the medical monitor will be notified. Participants who prematurely terminate from the study will not be replaced.

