5.4.7. Re-Entry into Study Treatment

In some circumstances, a participant may temporarily discontinue the study medication and/or not return to the study clinic for follow-up visits. If the participant decides to return for study treatment and/or follow-up assessments at a later date, he or she will be allowed and encouraged to do so.

The study will be conducted according to the intent-to-treat principle. This means that once randomized into the study, a participant will be expected to undergo all scheduled follow-up assessments and will remain in the assigned treatment group for purposes of statistical analysis regardless of the actual course of treatment administered. Withdrawal from treatment does not automatically entail withdrawal from the study. Withdrawal from the study will only occur if the participant dies or withdraws consent. Subjects who withdraw consent are classified as inactive but may again become active upon re-entry into the study, if they so choose.

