6.16. Stopping rules

As stated earlier, the progress of the study will be monitored by the DSMB which will review safety data and make recommendations regarding continuation, termination, or modification of the study. Based on a 12 month enrollment period and an additional study period of 12 months, the DSMB will formally review the safety data after participant number 24 reaches day 90 of the study. The number of subjects who discontinue study treatment will also be included in the reports prepared for the DSMB.

In addition, safety data will be reviewed by the DSMB when an event occurs that is of sufficient concern to the medical monitor and/or study investigator(s) to warrant review, or when an event occurs that contributes to a stopping rule listed below.

- **Patient stopping rules:** Subjects who have 3 severe hypoglycemic reactions (requiring assistance from another individual) on separate days or who have nausea or vomiting that precludes adherence to diet will discontinue the use of the study drug. Subjects who lose more than 10 kg will also discontinue study drug. Subjects who discontinue the drug treatment will not be replaced.
- **Trial stopping rules:** Interim analysis will be conducted when recommended by the DSMB to review safety data, including metabolic, immunological assessments and adverse events. The DSMB may recommend early stopping if there is sufficient evidence to conclude that the investigational treatment is harmful based on interim analysis of safety endpoints.

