7.1.5. Evaluation of Adverse events

A non-serious adverse event is an AE not classified as serious. Both serious and non-serious AEs should be graded with respect to severity on the following 3 point scale and reported, in detail, on the appropriate CRF page:

Mild	Discomfort noticed, but no disruption of normal daily activities; event usually requires no intervention.
Moderate	Discomfort sufficient to reduce or affect normal daily activities; even may require intervention.
Severe	Incapacitating, with inability to perform normal daily activities; event usually requires treatment or other intervention. Subject may not be able to continue in the study.

The Investigator should evaluate the relationship of each AE to the study treatment regimen, using the following criteria:

Unrelated:	Another cause of the AE is more plausible; a clinically plausible temporal sequence is inconsistent with the onset of the AE and administration of the study treatment regimen; or a causal relationship is considered biologically impossible.
Possibly related:	There is a clinically plausible time sequence between onset of the AE and administration of the study treatment regimen, but the AE could also be attributed to concurrent or underlying disease, or the use of other drugs or procedures. "Possibly Related" should be used when the study treatment regimen is one of several biologically plausible AE causes.
Definitely Related:	The AE is clearly related to use of the study treatment regimen.

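### The related-SAE criterion for stopping study drug in section 5.4.6 is circular: it is met only once treatment has already ended, so it never orders a stop

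*Combined protocol and SAP*

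**What the plan says.** Section 5.4.6 is written as a set of compulsory rules. Dosing "will be discontinued for an individual participant if any of the following criteria is met", and eight criteria follow. The fifth is "Any unexpected, treatment-related SAE resulting in permanent treatment discontinuation and not related to glycemic events".

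Other sections also bear on stopping drug after a serious event:

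- 5.4.1.3 (omega-3) ends treatment "should the investigator believes that the study treatment is no longer in the best interest of the participant".
- 5.4.5 removes a participant for a severe or serious AE that, "based on the medical judgment of the investigator, prevents completion of participation in the study".
- 6.16 repeats some objective rules for individual patients, for example "Subjects who lose more than 10 kg will also discontinue study drug".
- 7.1.6 requires SAEs to be sent to the medical monitor within 24 hours and reviewed by the DSMB. Section 11.1.3 describes the monitor as independent of the study.
- 6.14 convenes an ad hoc DSMB review after any death, or after related, unexpected SAEs of Grade 3 or higher in at least three participants.

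**The concern.** A stopping criterion should name an event and then order an action. This one names the event and the action together as its condition. Someone must first decide, on other grounds, to end treatment for good; only then is the criterion met, and nothing is left for it to order.

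The event is the one for which an individual stopping rule is most needed. The trial is titled a pilot safety and feasibility study, it doses children from age 6, and section 5.4.8 tells participants that there may be side effects not yet known. The list does compel a stop for weight loss above 10 kg and for nausea or vomiting that prevents adherence to diet. As written, it does not compel one for an unexpected serious event attributed to the treatment. A reader such as an IRB member could reasonably take the list to guarantee that stop.

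**Working it through.** No arithmetic applies beyond counting, and the plan states no figure to reproduce. The check has three steps.

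**Step 1: the logic of the criterion.** Let S be an unexpected, related, non-glycemic SAE and let D be permanent discontinuation of treatment. The rule reads: if S and D, then stop drug.

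- S true, D false (participant still on drug): the condition is false, so no stop is ordered.
- S true, D true (drug already stopped for good): the condition is true, but the stop has already happened.

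The rule adds no stop in either case. Reading the clause as an SAE that *requires* permanent discontinuation does not rescue it. Someone must still judge that discontinuation is required, and the best-interest criterion in the same list already covers that judgement.

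**Step 2: does another criterion in 5.4.6 order the stop?** The test case is a single non-fatal, non-glycemic, unexpected, related SAE.

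| 5.4.6 criterion | Reaches such an SAE of any type? | Orders a stop on the event itself? |
|---|---|---|
| Three severe hypoglycemic reactions | No (glycemic) | – |
| Nausea or vomiting preventing adherence to diet | Only if that is the event | – |
| Weight loss above 10 kg | Only if also present | – |
| Grade 3 or higher AE | Yes, if of that grade | No: judgement of investigator, medical monitor and trial physician |
| Unexpected related SAE | Yes | No: circular (step 1) |
| Participant's best interest | Yes | No: investigator's judgement |
| Participant's or representative's request | Only if they ask | – |
| Pregnancy | Only if also present | – |

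Three of the eight can reach the test case whatever the type of event, and 0 of those 3 order a stop on the event itself.

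**Step 3: does another section order it?**

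- 5.4.1.3 rests on the investigator's belief and concerns omega-3. Its one objective rule is chronic use of drugs that affect clotting, which is not an SAE rule.
- 5.4.5 rests on the investigator's medical judgement.
- The patient stopping rules in 6.16 cover hypoglycemia, nausea or vomiting, and weight loss.
- 6.14 starts a DSMB review, and for SAEs other than death its stated trigger needs three participants.
- 7.1.6 requires reporting and review, and states no stop of that participant's drug.

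So if the event meets no other objective criterion and the participant does not ask to stop, stopping drug rests on judgement alone.

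**The case against.** The strongest reply is that judgement-based stopping is a legitimate choice and that oversight is layered. The Grade 3 criterion just above the SAE one rests openly on the judgement of three parties, including the medical monitor. SAEs reach the monitor within 24 hours. Section 6.16 sends any event of sufficient concern to the DSMB, 6.13 lets the DSMB set its own triggers, and its charter (11.1.5) is not among the documents, so a single-SAE trigger cannot be ruled out. The products are over-the-counter supplements. All of this stands, and it limits the point to a missing compulsory rule. It does not make the criterion work: these are review and discretion processes, and the plan chose to list this event among compulsory stops.

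A second reply also stands. A permanent stop for every related SAE would be too blunt. Under 7.1.5, possibly related "should be used when the study treatment regimen is one of several biologically plausible AE causes", and 7.1.12 makes every overdose an SAE, including one for which correcting the dose may be enough. The remedy should therefore be an immediate stop with a controlled route back.

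A reader might infer more than the documents support:

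- *That the plan encourages restarting after a safety stop.* Section 5.4.7 does say of a returning participant that "he or she will be allowed and encouraged to do so", but it concerns temporary interruptions that end by the participant's own choice. It is silent on restarting after a safety stop.
- *That 6.15 keeps such a participant on drug.* It says that an ad hoc review does not by itself suspend dosing across the trial. It does not override an individual stop under 5.4.6.
- *That vitamin D has no stopping rule.* Section 5.4.2.2 offers only that "We will monitor blood levels of vitamin D to minimize the risk of these side-effects", but 5.4.6 governs all study drugs in every participant. For the same reason, the absence of the SAE criterion from 6.16 leaves no gap in coverage.

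**Conclusion.** The criterion is circular as written and cannot order a stop. For the test case, none of the three applicable criteria in 5.4.6 compels one, and no other section does. It is a stated safety rule that does not work. It should be corrected, but it does not show that serious events go unreviewed or that participants would in practice be kept on drug.

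The conclusion assumes a single event that is non-fatal, non-glycemic, unexpected and related, that meets no other objective criterion, in a participant who does not ask to stop. It also rests on the documents alone; the DSMB charter could add a review trigger. How many participants would be affected cannot be estimated, because no SAE rate is given. No sample size, power or type I error figure depends on the point.

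**What to change.** Amend the one criterion in 5.4.6. Delete the clause requiring that treatment has been permanently discontinued, and tie relatedness to 7.1.5, so that the criterion covers any unexpected SAE rated possibly or definitely related to study treatment and not related to glycemic events. Add that study drug is stopped at once for such an event and is not restarted unless the independent medical monitor agrees; without that agreement the stop is permanent. SAE, unexpected and the relatedness categories are already defined in 7.1.2, 7.1.3 and 7.1.5. The investigator still rates relatedness; the rule removes only the separate judgement on whether to stop. The DSMB provisions in 6.14 to 6.16 need no change.

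The cost is a short wording amendment and a few compulsory interruptions, some of them where another cause is plausible. These slightly reduce exposure to the assigned treatment. An overdose can be handled by correcting the dose and restarting with the monitor's agreement. Follow-up continues, and the intention-to-treat analysis set is unchanged.

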5.4.7. Re-Entry into Study Treatment

In some circumstances, a participant may temporarily discontinue the study medication and/or not return to the study clinic for follow-up visits. If the participant decides to return for study treatment and/or follow-up assessments at a later date, he or she will be allowed and encouraged to do so.

The study will be conducted according to the intent-to-treat principle. This means that once randomized into the study, a participant will be expected to undergo all scheduled follow-up assessments and will remain in the assigned treatment group for purposes of statistical analysis regardless of the actual course of treatment administered. Withdrawal from treatment does not automatically entail withdrawal from the study. Withdrawal from the study will only occur if the participant dies or withdraws consent. Subjects who withdraw consent are classified as inactive but may again become active upon re-entry into the study, if they so choose.

5.4.8. Risk to the Subjects

The risks of these over the counter drugs is summarize below:

- Omega-3 Fatty Acids may cause gastrointestinal side- effects including stomach pain or discomfort, burping, heartburn, vomiting, constipation, diarrhea, nausea, and change in the sense of taste. Joint pain may be a side effect as well.
- Vitamin D in very high doses can make the intestines absorb too much calcium which can cause high levels of calcium in the blood (hypercalcemia). This can cause side effects including nausea, vomiting, constipation, poor appetite, weakness, weight loss, confusion and disorientation. Hypercalcemia can also lead to kidney stones, damage to the kidneys, and cause calcium deposits in heart and lungs. We will monitor blood levels to minimize these risks.

Allergic reaction: As with any drug, it is possible that subjects could experience an allergic reaction to OMEGA-3, or Vitamin D. Such allergic reactions include: itching, skin rash, sudden drop in blood pressure, loss of consciousness and/or associated with seizures, including the possibility of death.

Blood draw risks: Drawing blood may cause temporary pain from the needle stick, bruising or swelling at the site, and rarely, infection or fainting.

Hypoglycemia: These medications could lower blood sugar too much (hypoglycemia). This could make subjects feel tired, dizzy, sweaty, and/or nauseated. Also, it could cause heart to feel as if it is racing. There may also be other effects. Untreated hypoglycemia could cause convulsions, loss of consciousness, and can lead to death. The clinical research team will provide added training and education to subjects to better manage hypoglycemia and other diabetes related complications.

Unknown Risks: The experimental drug may have side effects that no one knows about yet. The researchers will let you know if they learn anything that might make you change your mind about participating in the study.

Females of child bearing potential must have a negative pregnancy test prior to enrolling in the study and will be required to use at least two FDA approved birth control during the study. At every study visit the sexual activity of female participants of reproductive age will be re-assessed. Pregnancy testing will be conducted in females in reproductive age at 4, 8, 12 and 16 months study visit. If a subject who was previously sexually inactive becomes sexually active, she will be counseled about the need to use a reliable forms of birth control. Subjects will be requested to avoid pregnancy for 6 months following the last study administration and instructed to use birth control. If subject becomes pregnant, study intervention will be discontinued and subject withdrawn from study.

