7.1.11. Pregnancy

If, following initiation of the study product(s), it is subsequently discovered that a study subject is pregnant or may have been pregnant at the time of investigational product exposure, including up to 12 weeks after last product administration, the study product(s) will be permanently discontinued in an appropriate manner (e.g. dose tapering if necessary for subject safety).

They must be reported to the medical monitor within 24 hours by fax to [contact] with a confirmatory telephone call to [contact] and in accordance with SAE reporting procedures described above.

Any pregnancy that occurs in a female partner of a male study participant should be reported to the medical monitor.

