9.4.1. Analysis Populations

Analyses of study data will be conducted to address all objectives of the trial and other interrelationships among data elements of interest to the investigators and of relevance to the objectives of the study. Primary analysis of treatment effect will be conducted under the intention-to-treat principle of eligible patients whereby outcome data from all eligible patients will be included regardless of treatment compliance.

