9.7. Sample Size Considerations

Metabolic primary outcome

Sample size considerations correspond to the primary hypothesis which is that the proportion of patients with maintained or increased 90-min C-peptide at 12 months compared to baseline value is greater in the combination therapy group than in the vitamin D alone group. Standard power calculations for two sample tests of proportions indicate that 12 subjects in each group are needed to achieve 80% power to detect differences between less than 5% in the vitamin D alone group and at least 50% in the combination therapy group. Allowing for 10% dropout/attrition, sample size considerations include an allowance for 10% of the subjects to have missing data (one-year MMTT was not done or subject withdrew prior to the one-year assessment).

Primary endpoints should be available for all enrolled subjects. An exception will be if a death occurs or if the subject withdraws consent to be followed, although we expect this to be very limited. We also have included consideration for attrition in our design. Should there be any missing data, missing data will be assessed for mechanism of missingness and to see if missing at random assumptions are valid. If necessary, appropriate imputation strategies can be applied for sensitivity analysis. We will explore the data to assess if missingness at a given time point is related to observed data at the previous time point. If we find that, conditional on treatment group, observed values strongly predict subsequent values where observed, but are not related to missingness at subsequent time points, we may regard the missing data as a random sample of previously observed data.

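### Section 5.4.8 withdraws a participant who becomes pregnant from the study, while 5.4.6 asks her to stay in follow-up and 5.4.7 limits withdrawal to death or withdrawn consent

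*Combined protocol and SAP*

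**What the plan says.** Section 5.4.8, in its paragraph on contraception and pregnancy testing, sets the rule: "If subject becomes pregnant, study intervention will be discontinued and subject withdrawn from study". It names two separate actions, stopping the intervention and leaving the study. The same paragraph gives the test schedule: "Pregnancy testing will be conducted in females in reproductive age at 4, 8, 12 and 16 months study visit".

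Section 5.4.6 covers the same event. Its list of criteria for stopping study drug includes "The participant becomes pregnant", and the text after the list says: "The participant will be asked to remain in the study and participate in follow-up".

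Section 5.4.7, which sets out the intention-to-treat principle for study conduct, is exclusive: "Withdrawal from the study will only occur if the participant dies or withdraws consent".

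Section 5.4.1.3, under the omega-3 heading, likewise keeps those who stop treatment early in the study for both efficacy and safety assessments.

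Three other places touch the subject without settling it. Section 7.1.11 says that "the study product(s) will be permanently discontinued in an appropriate manner" and requires prompt reporting, but does not mention study withdrawal. Section 6.18, on pregnancy, is also silent on it. Section 9.7 expects the primary endpoint from everyone enrolled and adds: "An exception will be if a death occurs or if the subject withdraws consent to be followed".

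**The concern.** Sections 5.4.8 and 5.4.6 give opposite instructions for one event, and 5.4.7 rules out what 5.4.8 requires. Site staff would have to choose between them, and two cases could be handled differently.

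Two things are at stake if 5.4.8 is followed. The first is safety: section 4.1 defines the safety endpoint over two years, and withdrawal would end the scheduled adverse event assessments of a participant exposed to study product while pregnant. The pregnancy would still be reported under 7.1.11, and events already on record would still be followed under 7.1.1. The second is the primary endpoint: a randomised participant who is willing to continue would be removed because of a post-randomisation event and, if this happens before month 12, would have no one-year MMTT.

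**Working it through.** The plan has no figure on this point to reproduce. The check compares the rules, counts what 5.4.8 would cost, and then asks whether power is affected.

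**1. The rules side by side**

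| Section | Study drug after pregnancy | Participation in the study |
|---|---|---|
| 5.4.8 | stopped | ended |
| 5.4.6 | stopped | continues by request |
| 5.4.7 | not addressed | ends only on death or withdrawn consent |
| 5.4.1.3 | early stopping of treatment in general | continues, efficacy and safety |
| 7.1.11 | permanently stopped | not addressed |
| 6.18 | not addressed | not addressed |
| 9.7 | not addressed | endpoint expected, but a 10% allowance includes early withdrawal |

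The direct conflict is 5.4.8 against 5.4.6 and 5.4.7. Section 5.4.1.3 points the same way as those two. Section 9.7 fits retention but does not require it.

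**2. What 5.4.8 would cost before month 12**

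Inputs from Appendix A: six visits after baseline, at months 4, 8, 12, 16, 20 and 24; MMTTs after baseline at months 12 and 24. Tests come from 5.4.8.

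- Found at month 4: 6 − 1 = 5 later visits lost, with both MMTTs.
- Found at month 8: 6 − 2 = 4 later visits lost, with both MMTTs.

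In both cases the month-12 MMTT goes, and so does the primary endpoint. No loss is counted for the later tests. Appendix A dispenses drug only at visits 1 to 3 (baseline, months 4 and 8), so at month 12 treatment is ending and at month 16 it is over. It is unclear whether a sentence about stopping the intervention still applies then.

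**3. Power**

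Inputs: 5% against 50% (9.7) and 28 per arm (4.6). The 10% allowance is 0.10 × 28 = 2.8, so about 3 lost and 25 left per arm. Section 9.7 states neither alpha nor sidedness, so alpha = 0.05 is assumed and both versions are shown.

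Power = sum over all a and b of Bin(a; n, 0.05) × Bin(b; n, 0.50), counting only pairs with Fisher exact p ≤ 0.05.

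| n per arm | two-sided | one-sided |
|---|---|---|
| 28 | 0.9725 | 0.9870 |
| 25 | 0.9515 | 0.9807 |

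Losing three per arm, for any reason, costs 0.9725 − 0.9515 = 0.021 in the two-sided case. Losses to pregnancy within the plan's own allowance therefore leave power well above the stated 80%.

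**The case against.** The strongest reply is that withdrawal may be a deliberate safety choice. Section 6.18 excludes pregnant and lactating women, and exclusion 22 in 4.4.2 requires contraception throughout the study. The sponsor could repair the text the other way, by naming pregnancy as an exception in 5.4.6, 5.4.7 and 9.7. The cited provisions are mainly entry rules, however. Safety is served by stopping the product and leaving out unsuitable procedures; it does not call for ending safety visits. Keeping participants after they stop drug is also the rule that the protocol applies elsewhere.

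A second reply stands in large part: the event should be rare and the gain small. Half the sample is aged 6 to 17, only some participants are female, and 5.4.8 requires a negative entry test and two birth control methods. A month-12 MMTT may be judged unsuitable in pregnancy, or its C-peptide hard to interpret, so continued follow-up may recover little primary-endpoint data.

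A reader might infer more than the documents support:

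- *That 7.1.11 and 9.7 also contradict 5.4.8.* Section 7.1.11 is silent on study withdrawal. Section 9.7 states an expectation, and its 10% allowance expressly covers those who leave before the one-year assessment.
- *That the analysis population in 9.4.1 is breached.* It says that "outcome data from all eligible patients will be included regardless of treatment compliance". Withdrawal creates a missing outcome; it does not exclude collected data or change the assigned arm. The intention-to-treat wording that 5.4.8 offends is the follow-up rule in 5.4.7.
- *That the result would be biased.* With no pregnancy rate in the documents, neither size nor direction can be given.

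**Conclusion.** The contradiction is certain on the text, and its severity is minor. Sections 5.4.6 and 5.4.7 cannot be reconciled with the withdrawal clause of 5.4.8. Following that clause ends scheduled safety follow-up of a participant exposed during pregnancy. It also forfeits the one-year MMTT when pregnancy is found at the month-4 or month-8 test, or otherwise before month 12, without any withdrawal of consent.

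Few participants are likely to be affected, and the stated power is not threatened. The power check rests on the planning rates in 9.7 and an assumed alpha of 0.05. The inconsistency itself rests on no assumption.

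**What to change.** In 5.4.8, replace the clause that withdraws the participant with wording to this effect: she will be asked to remain in the study and in scheduled follow-up, with clinicians deciding which procedures, including the MMTT, are suitable in pregnancy. Stopping the study intervention stays as it is.

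In the analysis plan, add a sensitivity analysis of the primary outcome that leaves out C-peptide values taken during pregnancy.

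The cost is a protocol amendment, which 10.1 requires the IRB to approve before it takes effect, and one short extra analysis. The follow-up visits are already in the schedule. The remaining drawback is that the month-12 MMTT may be omitted on clinical grounds or be difficult to interpret, so the change secures safety follow-up more surely than it secures the primary endpoint.
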